### **Urine Pregnancy Test**

 Frequencies of urine pregnancy test result (positive / negative / not done) by visit

### **Exposure**

• Frequency distribution of number of infusions received

### **Concomitant medications**

- By-subject listing of past and concomitant medication including subject ID, site, medication generic name or therapy, dose, units, frequency, route, start date, end date, whether ongoing, indication.
- By-subject listing of Corticosteroid Therapy for Bullous Pemphigoid including subject ID, site, Corticosteroid Name, dose, units, frequency, route, start date, end date, whether ongoing.

### 9.4 Efficacy

All efficacy analyses will be done on efficacy population.

### 9.4.1 Main Efficacy Analysis

#### **Bullous Pemphigoid Disease Area Index (BPDAI)**

- Descriptive statistics of main efficacy endpoints listed in Section 7.2.1. (three activity sub-scores, Total Activity BPDAI score, Damage / Pigmentation sub-score, Total BPDAI score, change from baseline in Total Activity and Total BPDAI score, percent change from baseline in Total Activity and Total BPDAI score, categorized change in Total Activity score.).
- Mean plots for the Total Activity BPDAI score and Total BPDAI score over time
- If applicable, the covariate analysis will be done to examine the reduction over time in Total Activity BPDAI score and Total BPDAI score, adjusted for the baseline value. Specifically, the following model will be fit:

*Reduction at Visit* 4 = Baseline value,

This model will be applied on both change and percent change, for total activity and total BPDAI scores.

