The following assessments will be performed at the follow-up clinic visits except for Visit 9 (Day 118): physical examination (including weight), BPDAI including Pruritus VAS, physician's assessment of lesion healing, completion of ABQOL questionnaire, photography, vital signs, AE and concomitant medication recording and serum collection for BP180 and BP230 autoantibody titres, PK, blood sample collection for measurement of serum eotaxin-1 and anti-bertilimumab antibodies. Skin punch biopsy for H&E staining and eosinophil count in tissue will be conducted (Visit 5 only). Urine pregnancy test (Visit 5 and Visit 8) for females of childbearing potential only), PBMC biomarker blood sampling (Visit 5 only) and safety laboratory evaluations (hematology, biochemistry) will be performed (Visits 5 and 8 only). ECG will be performed at Visit 8 (Day 84). The only assessments that will be performed on Visit 9 (Day 118) are collection of concomitant medication and adverse event information, and semen analysis for males who have had abnormal semen analysis results at Visit 2 (Day 0) post-dose, Visit 3 (Day 14) or Visit 4 (Day 28) compared to baseline pre-dose Visit 2 results.

Corticosteroid usage will be documented and managed as necessary. Corticosteroid management can occur either during a scheduled visit, unscheduled visit, or phonecall follow-up based on the investigator's discretion.

Phone call follow-up (Approximately 2 and 4 months after Visit 8 (-Day 84)
The following assessments will be performed: completion of ABQOL questionnaire, adverse event assessment, and concomitant medication.
Corticosteroid usage will be documented and managed as necessary.

Study Duration

Study duration for each patient (following the screening period) will be up to approximately 204 days

Screening period: Up to 4 weeks

Treatment period: 28 days (\pm 2 days)

Follow-up period: 56 days (\pm 2 days) or 90 days (\pm 2 days) for males who have had abnormal semen analysis results post-dose Visit

_

 $^{^{}a,b}$ Study visits 3 through 9 have a ± 2 day window. The window is calculated from the actual visit day compared to baseline (Day 0), (e.g., for Visit 6 (Day 56) the window would be Day 54 to Day 58)

	2 (Day 0), Visit 3 (Day 14) or Visit 4 (Day 28) compared to pre-dose Visit 2 (Day 0) results; 2 and 4 months follow-up phone call after Visit 8 (Day 84).	
Number of Patients	Up to 15 patients are expected to be enrolled in this study. Recruitment will be competitive.	

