Change in PBMC biomarkers at Visit 5 compared to Visit 2 (Day 0)

Statistical Methods

This is an open-label study. Thus, only descriptive statistics and narratives of individual patient case studies are planned. All data collected on the case report forms (CRFs) will be summarized for the clinical study report (CSR).

All continuous parameters will be summarized using standard summary statistics as appropriate (n, mean, standard deviation, median, minimum, maximum, 25th percentile and 75th percentile). Summary statistics for categorical variables will include frequency counts and percentages. Summaries will be presented for all patients and by Treatment Phase and Follow-up Evaluation.

TABLE OF CONTENTS

PRO	OTO	COL SIGNATURE PAGE	2
PRO	OTO	COL VERSION HISTORY	3
PRO	OTC	COL SYNOPSIS	10
TAI	BLE	OF CONTENTS	21
GL	OSSA	ARY	24
1.0		TRODUCTION	
1.0		Bullous Pemphigoid	

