It has been demonstrated that relatively low doses of corticosteroids (e.g., 30 mg/day) are only partially effective in achieving disease control or complete remission. The rapid onset of steroid action is desired in order to alleviate patient symptoms as quickly as possible while the slower acting biologic takes effect. A key focus in this treatment is the goal is to taper the steroids as rapidly as possible, a difficult feat to achieve with steroids in isolation. Initial treatment with prednisone has therefore been added to bertilimumab treatment. This study is designed to demonstrate that the successful tapering of corticosteroids over a shorter period of time than physicians have been accustomed to will be possible with the administration of bertilimumab, thereby mitigating risks associated with long term steroid use.

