The study will consist of three periods:

- A screening period of up to 4 weeks
- An open-label treatment period lasting 4 weeks consisting of IV infusion of bertilimumab at Visit 2 (Day 0), Visit 3 (Day 14) and Visit 4 (Day 28)
- A safety and efficacy follow-up period of approximately 56 days (or 90 days for males who have had abnormal semen analysis results for post-dose Visit 2 (Day 0), Visit 3 (Day 14) or Visit 4 (Day 28) compared to pre-dose Visit 2 (Day 0) results); plus a follow-up phone call 2 and 4 months following Visit 8 (Day 84)

Due to the potential effects of long-term and/or high-dose systemic corticosteroid usage on bullous pemphigoid, newly diagnosed patients will be permitted to take systemic oral corticosteroids specifically for bullous pemphigoid only for a period of 4 weeks prior to the first treatment administration (Visit 2 - Day 0) at doses no greater than 40 mg/day prednisone equivalent.

Newly diagnosed patients who have taken systemic oral corticosteroid for bullous pemphigoid longer than 4 weeks prior to the first treatment administration (Visit 2 - Day 0) or at doses greater than 40 mg/day prednisone equivalent at any time are excluded from the study.

For newly diagnosed patients who have used systemic oral corticosteroids for reasons other than bullous pemphigoid, a washout period of 4 weeks prior to the first treatment administration (Visit 2 - Day 0) is required.

For newly diagnosed patients who are taking systemic oral corticosteroids at a daily dose between 40 mg/day and 30 mg/day prednisone equivalent for BP within 4 weeks prior to the first treatment administration (Visit 2 - Day 0), tapering of systemic corticosteroids will be conducted at the discretion of the investigator. However, patients must be on 30 mg/day prednisone equivalent for the first treatment administration (Visit 2 - Day 0). For newly diagnosed patients who are taking less than 30 mg/day prednisone equivalent prior to the first administration day (Visit 2 - Day 0), a stable dose of systemic corticosteroids should be maintained until Visit 2 (Day 0).

Patients who are resistant to corticosteroid tapering are not required to be washed out from oral corticosteroid treatment prior to Visit 2 - Day 0.

The tapering schedule depicted in Table 1 is recommended for the remainder of the study.

Systemic corticosteroid dose (prednisone equivalent) per day

≥30.0-10.1 mg/day

Decrease by 5 mg each week

10.0 − 0 mg/day

Decrease by 2.5 mg each week

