5.4 EFFICACY ASSESSMENTS

5.4.1 Bullous Pemphigoid Disease Area Index (BPDAI)

The BPDAI (See Appendix D) will be completed at all visits with the exception of Visit 9 (Day 118) as indicated in the Schedule of Events (Appendix A). At treatment administration Visits 2 (Day 0), 3 (Day 14), and 4 (Day 28), the BPDAI should be completed pre-dose (any time prior the initiation of treatment infusion). In screening, the BPDAI should be performed, if possible, prior to commencement of corticosteroid regimen.

The BPDAI Pruritus Component Visual Analogue Scale (VAS) will be completed by the patient or their legally authorized representative and all other sections for the BPDAI will be completed by the investigator. Patients and investigators will be asked to complete their respective sections on the corresponding worksheets, which will serve as source documentation for this measurement. The study source documents should reflect any issues that may have occurred during completion.

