## 4 Treatment Groups

This is a single arm trial, where all eligible patients will be treated with investigational product - Bertilimumab.

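### No planned efficacy output sets BPDAI beside prednisone within a patient, or summarises steroid exposure and BPDAI change between Screening and Day 0

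*SAP*

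**What the plan says.** - **BPDAI output.** SAP 9.4.1 gives descriptive statistics of scores, change, percent change and responder categories, plus "Mean plots for the Total Activity BPDAI score and Total BPDAI score over time". The one model written out has reduction at Visit 4 as outcome and the baseline value as its only term.
- **Prednisone output.** The same section gives prednisone its own tables and its own mean plots. Under SAP 7.2.1 (Prednisone Dose), a record that straddles Visit 2 is cut there, cumulative dose starts there, and dose reduction is counted from there.
- **Reference point.** SAP 6.2.2 has one baseline for everybody, the last value before the first infusion, and SAP 7.2.1 counts BPDAI change from it. Protocol 2.2 has two references: Visit 2 for newly diagnosed patients and Screening for taper-resistant patients.
- **Run-in.** Protocol 3.0 states: "newly diagnosed patients will be permitted to take systemic oral corticosteroids specifically for bullous pemphigoid only for a period of 4 weeks prior". That period ends at Day 0, and the daily dose may not exceed 40 mg. Protocol 5.4.1 adds: "In screening, the BPDAI should be performed, if possible, prior to commencement of corticosteroid regimen". Protocol 1.3 wants rapid steroid action to "alleviate patient symptoms as quickly as possible while the slower acting biologic takes effect".
- **Aim.** SAP 1.1 would judge efficacy in newly diagnosed patients by lower initial and cumulative steroid doses, with a rapid taper once lesions are first controlled. In taper-resistant patients it would judge efficacy by coming down on steroid with no flare, or by control at smaller doses.
- **Design.** SAP 4: "This is a single arm trial, where all eligible patients will be treated with investigational product". Protocol Synopsis: "Up to 15 patients are expected to be enrolled in this study".
- **Raw data.** SAP 9.3.2 lists corticosteroid therapy by subject with doses and dates, and SAP 10 lists all CRF data.

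**The concern.** The SAP's test of efficacy is a statement about two things in the same patient: the dose came down and the disease stayed controlled. Two mean curves, one for score and one for dose, do not show whether the patients who tapered are the patients whose skin stayed quiet.

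There is no control arm, and prednisone is expected to act before the antibody. The course before the first infusion is therefore useful context for reading what follows. A patient who began prednisone the day before Day 0 and one who had been on it for four weeks enter the efficacy tables alike. A reader of those tables cannot see whose score was already falling. At stake is how a small proof-of-concept result is read when the sponsor decides on further development.

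**Working it through.** The plan states no figure to reproduce: it gives no power, error rate or target effect. The check is a comparison of the texts, followed by illustrations.

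**1. What the planned outputs contain**

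| Question | Where | Answer |
|---|---|---|
| Score and dose joined within a patient? | SAP 9.4.1 | No table, figure or model term |
| Screening-to-Day 0 BPDAI change? | SAP 7.2.1, 9.4.1 | No; change runs from baseline to later visits |
| Steroid exposure before Day 0 summarised? | SAP 7.2.1 | No; summaries start at Visit 2 |
| Same reference as the protocol? | SAP 6.2.2, Protocol 2.2 | Yes for newly diagnosed, no for taper-resistant |
| Raw data available by patient? | SAP 9.3.2, 10 | Yes, in separate listings |

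**2. Dose falls by schedule.** Protocol Table 1, started at 30 mg/day and followed exactly, gives 25, 20, 15, 10, 7.5, 5, 2.5 and 0 mg/day at Days 7, 14, 21, 28, 35, 42, 49 and 56. Period means from Visit 2 to Visit 7 under the SAP rule are 27.5, 17.5, 8.75, 3.75, 0 and 0 mg/day. A falling mean-dose curve is therefore what the recommended taper produces. It becomes informative only when set against the same patient's disease.

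**3. Exposure left out of the summaries.** On that schedule the dose counted from Day 0 is 7 × (30 + 25 + 20 + 15 + 10 + 7.5 + 5 + 2.5) = 7 × 115 = 805 mg. A newly diagnosed patient who took 30 mg/day for the permitted 4 weeks beforehand had 28 × 30 = 840 mg that is not counted. A patient who started just before Day 0 had almost none.

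**4. What a run-in can hide (assumed model).** Suppose the score halves every h days on prednisone alone and bertilimumab does nothing: reduction = 1 − 0.5^(t/h).

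| h (days) | Day 0 to 42 | Day 0 to 84 | Day −28 to 0 | Day −14 to 0 |
|---|---|---|---|---|
| 14 | 88% | 98% | 75% | 50% |
| 28 | 65% | 88% | 50% | 29% |
| 42 | 50% | 75% | 37% | 21% |
| 56 | 41% | 65% | 29% | 16% |
| 84 | 29% | 50% | 21% | 11% |

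The first two columns appear in the SAP's change tables; the last two do not. The half-lives are assumptions, and the model ignores any loss of steroid effect during the taper. If 15 patients are evaluable, each is 1/15 = 6.7 percentage points of a responder rate.

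**5. Reference point for a taper-resistant patient (assumed scores at Screening, Day 0, Day 42).**
- 60, 40, 20: from Day 0, (40 − 20)/40 = 50%; from Screening, (60 − 20)/60 = 67%.
- 40, 60, 30: from Day 0, (60 − 30)/60 = 50%; from Screening, (40 − 30)/40 = 25%.

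The second patient is a 50% responder under the SAP and not under the protocol.

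**6. How far a prior trend can be read.** Take 60 at Day −28, 40 at Day 0 and 20 at Day 42. In points, the fall is (60 − 40)/28 = 0.71 per day before and (40 − 20)/42 = 0.48 after. In proportion, it is ln(60/40)/28 = 0.0145 per day before and ln(40/20)/42 = 0.0165 after. The ordering reverses with the scale, and the responder endpoint is proportional. Displaying the trend is useful, but it does not settle which drug produced the later fall.

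**The case against.** **The results are not only group means.** A reader might infer that they are, and that improvement before and after Day 0 cannot be told apart at all. The documents do not support that. SAP 9 plans standard deviations, medians and ranges. SAP 7.2.1 and 9.4.1 plan responder counts and a frequency table for 10 mg/day or less, and the listings allow each patient's course to be rebuilt. This stands, and it narrows the point to the absence of a combined display. The listings are a weak substitute: prednisone sits on one of two forms depending on protocol version, and must be matched by date to the scores.

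**Day 0 is the protocol's own reference for newly diagnosed patients.** This stands. The departure concerns taper-resistant patients only.

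**Screening may be in the mean plots.** SAP 9.4.1 does not exclude it, whereas the laboratory section excludes it expressly. Its absence cannot be asserted. Even if it is plotted, a group mean hides differing steroid start dates.

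**Narratives.** The Protocol Synopsis says "only descriptive statistics and narratives of individual patient case studies are planned". Protocol 8.0 and the SAP do not mention narratives. A reader might infer that they were cancelled, but silence does not show that.

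**Screening scores may be missing.** Per the protocol version history, version 4.0 had BPDAI at all visits except Screening, and version 6.0 added it there. SAP 6.2.1 refers to 4-hour PK samples under some protocol versions, and version 5.0 moved 4-hour assessments to 2 hours. Some patients were therefore apparently treated before Screening BPDAI was required. Even now the pre-steroid score is sought only where possible. This stands, and the fix must allow for it.

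**The study is small and descriptive, and SAP 9.7 and 9.8 allow further exploratory analyses.** True, but neither section names this display.

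**Conclusion.** The point holds as a gap in the planned efficacy outputs. Score and dose are never joined within a patient, and the interval from Screening to Day 0 is not summarised, although the SAP's own efficacy criterion needs the first and the protocol seeks data for the second. There is also one departure from the protocol: the BPDAI reference for taper-resistant patients.

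The documents do not fix its size. Under the assumed steroid-only model, reductions from Day 0 to Day 42 run from 29% to 88%, beside falls of 21% to 75% in the preceding 28 days that the change tables would not contain. These figures rest on the assumed half-lives and on a constant rate of decline through the taper.

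A reader might go further and expect the added displays to show which responses are not due to bertilimumab. They cannot. With one arm and prednisone given alongside, a prior trend is context and not attribution. The change is worth making because it is specific and cheap. It does not touch the primary safety objective.

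**What to change.** In SAP 9.4.1:

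1. Add a per-patient table with subgroup, days on systemic steroid before Day 0, Day 0 dose, and Total Activity at Screening and Day 0 with their change. Mark patients who have no Screening score or no pre-steroid score.
2. Add one profile per patient from Screening, where available, to Visit 8. Put Total Activity and daily prednisone-equivalent dose on one time axis, with infusions, rescue and flares marked.
3. Give BPDAI change from Screening for taper-resistant patients, as Protocol 2.2 states, or justify the departure.
4. State that change from Day 0 in a patient who started steroid during screening is not by itself evidence of a bertilimumab effect. State also that the profiles show a prior trend but cannot attribute later change to either drug.

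The cost is at most 15 figures and one table, built from data the SAP already plans to list. Screening values will be missing for some patients, and under the SAP's no-imputation rule they should be shown as missing.

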## 1.2 Study Design Configuration

This is an open-label, proof-of-concept, single group study in newly diagnosed adult patients and adult patients resistant to corticosteroid tapering with moderate to extensive BP.

The study will consist of three periods:

- A screening period of up to 4 weeks
- An open-label treatment period lasting 4 weeks consisting of IV infusion of bertilimumab at Visit 2 (Day 0), Visit 3 (Day 14) and Visit 4 (Day 28)
- A safety and efficacy follow-up period of approximately 56 days plus a follow-up phone call 2 and 4 months following Visit 8 (Day 84)

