### Total BPDAI Score

**Total BPDAI** score is defined as sum of the Total Activity scores and BPDAI Damage / Pigmentation Score. Higher scores indicate greater disease activity.

• Change in **Total Activity Score** of BPDAI from Baseline to all subsequent visits

Change in Total Activity Score =

(Baseline Total Activity BPDAI - Visit *t* Total Activity BPDAI)

• Change in Total BPDAI Score from Baseline to all subsequent visits

Change in Total BPDAI Score = (Baseline Total BPDAI - Visit t Total BPDAI)

Note: larger positive difference indicates greater improvement.

 Percent change in Total Activity Score of BPDAI from Baseline to all subsequent visits

Percent Change in Total Score = 100\*(Baseline Total Activity BPDAI – Visit t Total Activity BPDAI) / Baseline Total Activity BPDAI

Percent change in Total BPDAI Score from Baseline to all subsequent visits
 Percent Change in Total BPDAI Score = 100\*(Baseline Total BPDAI – Visit t Total BPDAI) / Baseline Total BPDAI

Note: larger positive difference indicates greater improvement.

In addition, percent change in Total Activity score of BDPAI will be further divided into 4 categories:

- 1. # subjects with >= 90% reduction in BPDAI total activity score
- 2. # subjects with >=75% reduction in BPDAI total activity score
- 3. # subjects with >=70% reduction in BPDAI total activity score
- 4. # subjects with >= 50% reduction in BPDAI total activity score

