### **Physical Examination**

- Frequency distribution of evaluation (normal/abnormal non-clinically significant (NCS)/abnormal clinically significant (CS)/not done) by body system and visit.
- By-subject listings of CS abnormal physical examination results, including patient ID, Center, Visit, Body System and Abnormality Description.
- Shift table of normal/abnormal non-clinically significant (NCS)/abnormal clinically significant (CS) transitions from Screening to Visit 4 (last infusion) and Visit 8 (last planned FU).

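### Does SAP 9.4.1 need changing because its baseline-adjusted BPDAI model names Visit 4 only, when its stated aim is reduction over time?

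*SAP*

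**What the plan says.** Under the BPDAI heading, SAP 9.4.1 lists three items. The first is descriptive statistics of the endpoints defined in 7.2.1. The second is mean plots of the Total Activity and Total BPDAI scores across visits. The third, introduced as conditional, is a regression: "the covariate analysis will be done to examine the reduction over time in Total Activity BPDAI score and Total BPDAI score", with baseline as covariate. The model is printed as "Reduction at Visit* 4 = Baseline value". The next sentence sets its scope: "This model will be applied on both change and percent change, for total activity and total BPDAI scores". That sentence widens the model to two scores and two metrics and does not mention visits.

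SAP 7.2.1 defines the outcomes more broadly. One endpoint is "Change in Total BPDAI Score from Baseline to all subsequent visits", and the matching Total Activity change is written as "Baseline Total Activity BPDAI - Visit *t* Total Activity BPDAI", with a general visit index.

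Two passages bear on what Visit 4 is. SAP 1.2 describes "IV infusion of bertilimumab at Visit 2 (Day 0), Visit 3 (Day 14) and Visit 4 (Day 28"), so Visit 4 is the last infusion visit. Protocol 5.4.1 says that at treatment visits "the BPDAI should be completed pre-dose (any time prior the initiation of treatment infusion"), so the Visit 4 score is taken before that infusion.

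SAP 9.8 makes covariate analysis exploratory and dependent on a sponsor request. Protocol 8.0 plans descriptive statistics only.

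**The concern.** An aim about the course of the score over time cannot be met by a regression at a single visit. As printed, the model leaves out Visits 3, 5, 6, 7 and 8. The BPDAI responder endpoint in Protocol 2.2 uses Visits 5 to 8, and its change endpoint uses every scheduled measurement. Visit 4 is therefore not a responder visit, and it reflects only two of the three infusions. No passage says why it was chosen.

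This is also the only model that the SAP writes out, and it sits under the main efficacy analysis. If the single-visit fit were the sole basis for a statement about BPDAI reduction, the statement would stop at Day 28 of an 84-day course. SAP 7.4 refers to the study as already completed, so a visit chosen without a stated reason could be taken for one chosen after seeing the data.

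**Working it through.** No sample size, error rate or effect size is stated for this analysis, so there is no figure of the plan's to reproduce. The check compares the passages, counts fits, and asks what a wider model would add.

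**Visits.** From the schedules (Protocol Appendix A, SAP section 5), BPDAI is scored after baseline at Visits 3, 4, 5, 6, 7 and 8, on Days 14, 28, 42, 56, 70 and 84. That is 6 visits, of which the printed model uses 1. The span after Visit 4 is 84 − 28 = 56 days, and 56/84 = 67% of the course.

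**Fits.**
- As printed: 2 scores × 2 metrics × 1 visit = 4.
- At every post-baseline visit: 2 × 2 × 6 = 24.
- Absolute change only, at every visit: 2 × 6 = 12.
- Residual degrees of freedom per fit, with intercept and baseline: at most 15 − 2 = 13.

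**Two readings of the index.**
- *It should be t.* SAP 7.2.1 uses an italic t for the same quantity. In the machine-read text of 9.4.1 the italics stop just before the 4 and the line ends in a stray comma. These signs fit a misread or mistyped symbol but do not prove one. On this reading aim, endpoint and model agree, and the analyst fits each visit in turn.
- *It is 4.* Visit 4 is a landmark elsewhere in the SAP: the physical examination shift tables in 9.3.2 use "transitions from Screening to Visit 4 (last infusion) and Visit 8 (last planned FU"). On this reading the model describes the reduction from Day 0 to Day 28, and the aim is loosely phrased.

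**What fitting every visit would add.** Let y be the reduction at a visit and x the baseline score. Least squares gives intercept a = ȳ − b·x̄. The fitted mean at the average baseline is a + b·x̄ = ȳ, the raw mean reduction. This is exact, for change and for percent change. So with complete data the adjusted estimate at each visit is the figure already in the by-visit table.

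**With patients missing at a visit.** If k of n patients are missing, the estimate at the full-population mean baseline differs from the raw mean by b × (x̄_all − x̄_obs), where x̄_all − x̄_obs = (k/n)(x̄_missing − x̄_obs). The documents give neither b nor the baseline SD. Assume a gap of 0.5 baseline SD between the full and observed means:
- 3 of 15 missing: (3/15)·δ = 0.5, so δ = 2.5 SD.
- 5 of 15 missing: (5/15)·δ = 0.5, so δ = 1.5 SD.

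Here δ is how far the missing patients' mean baseline must lie from that of the observed patients. Even a half-SD gap therefore needs a strongly selected group of dropouts.

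**What already covers the later visits.** The 7.2.1 change and percent-change endpoints run from baseline to all later visits, and 9.4.1 summarises them. The mean plots show the course of both scores. SAP section 10 lists all CRF data by patient.

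**The case for a change.** The strongest case for acting is that the inconsistency is visible, is cheap to settle, and concerns the one model that the SAP spells out. If the source document does read 4, either the visit or the description of the aim is inexact, and a line of text would cure it. The model gives no reason for Visit 4, and that visit precedes the third infusion and all four responder visits.

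The observation stands: as printed, the aim and the model do not match. It does not stand that an analyst is left without instruction. Followed literally, the text fixes one visit, one covariate, two scores and two metrics. Read in line with 7.2.1, it fixes the same regression at each visit. Nor is the result limited to Day 28, because the by-visit summaries run to Day 84 whichever reading is taken.

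Model-based intervals or a repeated-measures model would go beyond reconciling one symbol. SAP section 9 plans no intervals for these summaries, and anything added now would be post hoc. The choice between Screening and the last pre-treatment value as baseline affects every BPDAI change. It is a separate matter and does not bear on the visit index.

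**Conclusion.** No change to the plan follows. This is a clerical point about one symbol, and at most it merits a look at the source document to confirm whether the index is t or 4. The model is conditional in 9.4.1 and exploratory, on sponsor request, in 9.8. The study is single-arm with up to 15 patients, and the protocol plans only descriptive statistics. No test, error rate, safety result or decision rule depends on the model.

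Extending it would raise the count from 4 fits to 24 (12 for absolute change only). With complete data it would return point estimates identical to the tabulated means. The conclusion rests on three things: the by-visit summaries being produced for all visits as 7.2.1 and 9.4.1 provide, the model keeping its exploratory status, and missing patients not being so different at baseline that adjustment moves a visit mean appreciably. The third cannot be sized in BPDAI points from the documents. If it failed, the descriptive results at that visit would need the same caution with or without this model.
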